## 1. Background and Rationale

Hyperbaric oxygen therapy (HBOT) involves breathing 100% oxygen at pressures greater than atmospheric pressure. Prior research suggests HBOT may improve cardiovascular fitness and modulate inflammatory processes. While higher pressures such as 2.0 ATA have demonstrated physiologic benefits, they may be associated with increased risk and cost. Lower pressures may provide fewer benefits. Intermediate pressures, such as 1.75 ATA, remain underexplored. This study aims to evaluate whether HBOT at 1.75 ATA improves aerobic capacity and inflammatory biomarkers while maintaining an acceptable safety profile.

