## 2. Study Objectives

Primary Objective: To assess changes in VO2 max following HBOT at 1.75 ATA.

Secondary Objective: To evaluate changes in circulating inflammatory cytokine profiles following HBOT at 1.75 ATA.

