## 6. Outcome Measures

Primary Outcome: Change in VO2 max measured via cardiopulmonary exercise testing.

Secondary Outcomes: Changes in circulating inflammatory cytokines measured from venous blood samples.

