## 7. Study Procedures and Timeline

Assessments will occur at baseline, mid-intervention, immediately post-intervention, and approximately four weeks after completion of HBOT. Assessments include VO2 max testing, blood sample collection, and vital sign monitoring.

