## 9. Safety Monitoring and Ethics

Participants will be screened for contraindications prior to enrollment and monitored throughout the study. Adverse events will be documented and reviewed by the study team. The study has received approval from an Institutional Review Board, and all participants will provide written informed consent prior to participation.

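### Does the safety clause in the Section 1 aim require a matching safety objective and outcome?

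*Protocol*

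**What the plan says.** Section 1 (Background and Rationale) states the aim in a single sentence: "This study aims to evaluate whether HBOT at 1.75 ATA improves aerobic capacity and inflammatory biomarkers while maintaining an acceptable safety profile". The clause at issue is its last: "while maintaining an acceptable safety profile". The same section says of higher pressures that "they may be associated with increased risk and cost", so safety is part of the reason for studying an intermediate pressure.

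Section 2 has one primary objective, on VO2 max, and one secondary objective: "Secondary Objective: To evaluate changes in circulating inflammatory cytokine profiles following HBOT at 1.75 ATA". Section 6 matches it, with VO2 max as primary and, below it, "Secondary Outcomes: Changes in circulating inflammatory cytokines measured from venous blood samples". Neither section mentions safety.

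Safety appears in two later places. The assessments in Section 7 include "blood sample collection, and vital sign monitoring". Section 9 has participants screened for contraindications and "monitored throughout the study", and adds: "Adverse events will be documented and reviewed by the study team". Section 8, the statistical overview, names no safety analysis.

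**The concern.** The sentence in Section 1 reads as a study question, not as background colour. It says the study will evaluate something, and safety is one of the things named. A reader who turns to the objectives and outcomes expects all three parts there and finds two. The word *acceptable* also implies a judgement, and the protocol gives no criterion for it. The design in Section 3 is single-arm, so no concurrent group supplies a reference either.

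At stake would be the safety conclusion of the eventual report. With no named outcome and no stated basis, the study team could look at the events that occurred and then declare the profile acceptable. Objectives and outcomes belong in a protocol, so an analysis plan would not obviously supply the missing lines.

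**Working it through.** The point is textual, so the check compares the sections.

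| Part of the Section 1 aim | Objective in Section 2 | Outcome in Section 6 | Data collected |
|---|---|---|---|
| Aerobic capacity | Yes, primary | Yes, primary | VO2 max testing (Section 7) |
| Inflammatory biomarkers | Yes, secondary | Yes, secondary | Blood samples (Section 7) |
| Safety | None | None | Vital signs (Section 7); adverse events (Section 9) |

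1. *Is the mismatch there?* Yes. Section 1 has three parts, and Sections 2 and 6 each carry two. No section defines *acceptable*.

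2. *Do the governing sections conflict with each other?* No. Sections 2 and 6 agree line for line. The odd one out is a trailing clause in the rationale.

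3. *Does the protocol fix a safety analysis that would mislead?* No. It states no safety hypothesis, test, margin or threshold, so there is no rule to apply wrongly.

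4. *Would safety go unreported for lack of data?* No. Participants are followed for the whole study, and adverse events are documented without being tied to an outcome. The assessment about four weeks after the last session falls within that follow-up. A descriptive listing, or the proportion of participants with an event, needs nothing further to be collected.

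5. *Would closing the mismatch change a result?* There are two routes. Deleting the clause changes no analysis. Adding a descriptive safety line to Sections 2 and 6 would formalise a summary that an analyst would produce anyway. Neither touches VO2 max or the cytokines.

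6. *Can the consequence be given a number?* Not from the protocol, which states no sample size. One can show how wide an exact interval would be at assumed sizes. With no events among n participants, the two-sided 95% upper limit is 1 − 0.025^(1/n):
   - n = 10: 30.8%
   - n = 20: 16.8%
   - n = 50: 7.1%

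   These figures describe how little a small study can exclude. They would be the same whether or not Section 2 listed a safety objective, so they do not measure the mismatch.

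**The case for a change.** The strongest case for acting runs as follows. The clause is not decorative, because safety helps to justify the chosen pressure and readers will expect a conclusion on it. Collecting data is not the same as naming an outcome. Leaving the judgement until the data are in invites a favourable reading, and the illustrative limits show that even an event-free small study would leave a sizeable event proportion possible. The remedy costs a line or two.

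Part of this stands. The three sections do not line up, the missing objective is protocol content, and a bare statement that safety was acceptable would be weakly supported. Three things take the force out of it:

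- The missing objective and the missing definition are separate matters. The second could be supplied in an analysis plan, which may exist and is not at hand. It therefore cannot be asserted that the judgement would be made only after the data are seen.
- Nothing in the protocol commits the team to a formal verdict on safety. The caution that a small single-arm study needs is a matter for how the report is worded, and it applies with or without a listed objective.
- A specified outcome is not automatically an improvement. The proportion of participants with an event during the treatment course, for example, would leave out the follow-up about four weeks later, which the protocol's monitoring includes. It would also leave the undefined word standing in Section 1.

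**Conclusion.** The observation is accurate but calls for no change to the plan. It is a minor mismatch between one clause of the rationale and two sections that agree with each other. Its extent is one of three parts of the aim not carried into the objectives and outcomes. Its effect on the VO2 max and cytokine results is nil. The gap in safety reporting is one that analysts fill as a matter of course, by summarising adverse events descriptively over the monitored period from data the protocol already has collected.

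This rests on two assumptions: that the adverse events documented under Section 9 will be reported, as is ordinary practice, and that the report will not present *acceptable* as a tested finding. The protocol contains nothing that points the other way.

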## 2. Study Objectives

Primary Objective: To assess changes in VO2 max following HBOT at 1.75 ATA.

Secondary Objective: To evaluate changes in circulating inflammatory cytokine profiles following HBOT at 1.75 ATA.

## 3. Study Design

This is a prospective, single-arm, pre–post interventional study. Participants will undergo baseline assessments, receive HBOT intervention, and complete follow-up assessments at prespecified time points.

## 4. Study Population

The study will enroll physically active adults aged 30 to 60 years. Participants must be generally healthy and capable of completing maximal exercise testing. Individuals with medical contraindications to HBOT or exercise testing will be excluded.

## 5. Intervention

Participants will undergo 24 hyperbaric oxygen therapy sessions over approximately eight weeks. Each session consists of exposure to 100% oxygen at 1.75 ATA for 100 minutes, including scheduled air breaks. All sessions will be conducted in a supervised clinical hyperbaric facility.

## 6. Outcome Measures

Primary Outcome: Change in VO2 max measured via cardiopulmonary exercise testing.

Secondary Outcomes: Changes in circulating inflammatory cytokines measured from venous blood samples.

## 7. Study Procedures and Timeline

Assessments will occur at baseline, mid-intervention, immediately post-intervention, and approximately four weeks after completion of HBOT. Assessments include VO2 max testing, blood sample collection, and vital sign monitoring.

## 8. Statistical Analysis Overview

Within-participant changes will be analyzed using paired statistical methods. Continuous outcomes will be summarized using descriptive statistics. Statistical significance will be assessed using appropriate parametric or nonparametric tests based on data distribution.

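### Optional, low-cost improvement: a baseline-to-later paired test of VO2 max leaves out the mid-intervention value of participants without the later visit; a repeated-measures model would use it

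*Protocol*

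**What the plan says.** Protocol section 8 states the method in general terms: "Within-participant changes will be analyzed using paired statistical methods", and "Statistical significance will be assessed using appropriate parametric or nonparametric tests based on data distribution". It names no specific test, does not say that participants with incomplete data are excluded, and does not rule out imputation before a paired test.

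Section 7 sets four occasions: "Assessments will occur at baseline, mid-intervention, immediately post-intervention, and approximately four weeks after completion of HBOT". It lists VO2 "max testing, blood sample collection, and vital sign monitoring" as the assessments. It does not assign tests to visits, so a mid-intervention VO2 max is the plain reading, not an explicit statement.

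Section 6 makes the primary outcome the change in VO2 "max measured via cardiopulmonary exercise testing" and names no time point. Section 3 reads: "This is a prospective, single-arm, pre–post interventional study". Section 5 reads: "Participants will undergo 24 hyperbaric oxygen therapy sessions over approximately eight weeks".

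The protocol gives no sample size, SD, significance level, dropout rate or expected reason for leaving.

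**The concern.** In a single-arm study the within-person change is the whole primary estimate. No comparison arm exists in which selective leaving might partly cancel. Treatment runs for about eight weeks and the last visit is about four weeks after that, so some participants may have a mid-intervention VO2 max but no later one. A paired baseline-to-later test cannot use what is known about them.

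If poor responders at mid-intervention are the ones who leave, the mean change in those who remain is too high. If good responders leave, it is too low and power falls. If leaving has nothing to do with response there is no bias, and the only loss is a little precision. The mid-intervention value is the information that could correct the first two cases, and on the plain reading of section 7 it is already being collected.

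**Working it through.** **Inputs.** From the protocol: one arm, four visits, paired analysis of change. It states no power or sample-size figure, so there is nothing to reproduce. Everything else is assumed:
- n = 15-30 and a two-sided 5% test;
- SDs of 6 (between persons), 2 (response) and 1.5 (measurement) mL/kg/min;
- half of the response present at mid-intervention;
- leavers miss both later visits;
- contrast from baseline to immediately post-intervention.

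**Step 1: when bias arises.** Bias of the mean change among those with both values = Cov(completion, change) / P(completion). It is zero if completion is unrelated to change.

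**Step 2: implied spread and correlation.** The between-person SD cancels in a change.
- Variance of the post change: 2² + 2 × 1.5² = 8.5, SD 2.92. SE at n = 20: 2.92/√20 = 0.65.
- Variance of the mid change: 1² + 2 × 1.5² = 5.5.
- Covariance: 0.5 × 2² + 1.5² = 4.25.
- Correlation: 4.25/√(5.5 × 8.5) = 0.62.

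**Step 3: upper bound.** If the fraction d with the lowest mid change all leave, bias = ρ·φ(z_d)/(1−d) SD. With ρ = 1 this is 0.109 SD at 5% and 0.195 SD at 10%. With ρ = 0.62 and SD 2.92 it is 0.109 × 0.62 × 2.92 = 0.20 and 0.195 × 0.62 × 2.92 = 0.35 mL/kg/min.

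**Step 4: graded leaving, true change 0.** Simulation with 10,000 runs per setting. Leaving is logistic in the observed mid change; the weak link is a slope of 0.5 per SD, the strong link 1.5 (an odds ratio of e^1.5 ≈ 4.5 per SD). Results for the paired t-test over n = 15-30 (bias in mL/kg/min, size only for the strong link, which was run in both directions):

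| Dropout | Weak: bias | Weak: rejection | Strong: bias | Strong: rejection |
|---|---|---|---|---|
| 5% | 0.04-0.05 | 5.1-5.3% | 0.11-0.13 | 5.3-5.7% |
| 10% | 0.08-0.10 | 5.2-5.3% | 0.21-0.23 | 5.9-6.8% |
| 15% | 0.12-0.14 | 5.3-5.6% | 0.31-0.32 | 6.4-8.5% |
| 25% | 0.21-0.22 | 5.5-6.2% | 0.49-0.51 | 8.5-12.7% |

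With unrelated leaving, bias is within 0.01 of zero and rejection is 4.7-5.3%. Monte Carlo error is about 0.005-0.009 for bias and 0.2-0.3 percentage points for rejection.

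A separate simulation in SD units (odds ratios 1.5-3 per SD, ρ = 0.5-0.7) agrees: bias 0.011-0.037 SD at 5% dropout and 0.022-0.069 SD at 10%. The SE is 0.14-0.22 SD at n = 50-20.

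**Step 5: the all-visit model in the same settings.** Unstructured REML with Kenward-Roger degrees of freedom: bias within 0.011, rejection 4.9-6.5% (the highest at n = 15, 25% dropout).

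**Step 6: leaving that depends on what was not observed.** Slope 1.5, 15-25% dropout:
- driven by true response: paired 0.34-0.56, model 0.22-0.36;
- driven by the unseen later change: paired 0.51-0.81, model 0.33-0.54.

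About two thirds of the bias remains (for example 0.36/0.56 = 64%).

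**Step 7: power.** True change 1.5, high responders leave, strong link. Paired against model: at 10% dropout, 44% against 55% (n = 20) and 62% against 75% (n = 30); at 20% dropout, 31% against 51% and 45% against 71%. Power was computed only for this direction, which favours the model.

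**The case against.** The strongest objection is scope. Section 8 is an overview; the model, covariance structure and missing-data handling usually belong in the SAP, which may exist and may already specify a repeated-measures model. A reader might infer that the protocol commits to a completers-only analysis, or that the primary result will be biased. Neither is supported: no exclusion rule is stated, imputation before a paired test would fit the wording, and bias needs a link between leaving and response that the protocol gives no reason to expect. What survives is narrower: section 8 does state a method, and for the visits in section 7 another one uses more of the data at little cost.

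The second objection is size, and it largely stands. All driving inputs are assumed. With the weak link at 10% dropout, the bias is about 0.09/0.65, one seventh of the standard error at n = 20. The material results need 15-25% dropout together with an odds ratio of about 4.5 per SD. Nothing in the protocol points to dropout that high among generally healthy, active adults.

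Third, the model has its own assumptions. It estimates the change for leavers as if they had resembled those who stayed with similar observed values, and this choice of estimand should be acknowledged. It also leans on approximate normality, while section 8 allows nonparametric tests. Both points stand and are carried into the fix as stated assumptions and sensitivity analyses.

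**Conclusion.** Worth considering as a cheap improvement, not a defect that invalidates the plan. A baseline-to-later paired test does leave out the mid-intervention VO2 max of anyone without the later value. The effect on bias and false positives is nil if leaving is unrelated to response, small at 5-10% dropout, and material only at about 15-25% with a strong link. Power can be affected sooner, at 10% dropout, but only if it is strong responders who leave.

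The conclusion rests on three readings: VO2 max is measured at mid-intervention, the primary change is to a visit after it, and the paired test is applied to observed pairs. It concerns the later-visit change only; a separate baseline-to-mid comparison would still use the mid value. Confidence is medium, because every quantity behind the sizes is assumed.

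**What to change.** In section 8, replace the sentence on paired methods, for VO2 max, with text such as:

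> VO2 max at all visits will be analysed with a likelihood-based repeated-measures model (visit as a categorical fixed effect, unstructured within-participant covariance, Kenward-Roger degrees of freedom), including every participant with a baseline value. The primary contrast is baseline to immediately post-intervention, reported with a 95% CI. The analysis assumes that data are missing at random given the observed visits. If the model does not converge, it will be refitted with unstructured covariance to baseline, mid-intervention and the primary later visit.

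If the SAP names another primary contrast, use that one; the contrast must be written out because section 6 does not name it. Keep the paired t or Wilcoxon test as a sensitivity analysis, and add a missing-not-at-random analysis that shifts the imputed later values of leavers over a stated range. If the SAP already specifies such a model, align section 8 with it.

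**Cost.** Wording and modest extra analysis; no added visit or test on the plain reading of section 7.
- With complete data the estimate, standard error and degrees of freedom equal those of the paired t-test (checked at n = 20, 19 df).
- Under the strong link the estimator SD rises by about 1% at 5% dropout, 1-3% at 10%, 2-5% at 15% and 5-9% at 25%. With unrelated leaving it falls by about 1-4%.
- Rejection can sit slightly above nominal at very small n with high dropout (up to 6.5%). With heavy-tailed data (t, 5 df) it was 4.9-5.9%.
- The three-visit fallback gave bias within 0.009 and rejection of 5.0-6.2% at 15-25% dropout. Compound symmetry should not be the fallback: its rejection was 8.9-9.7%, and about 35% of the paired bias remained under the strong link.
- Convergence was tested only for dropout after the mid visit; scattered missing visits were not tested.
- Someone who leaves before the mid visit contributes only a baseline. Correction is partial if leaving depends on unobserved response, and the lack of a control group is not addressed.

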## 9. Safety Monitoring and Ethics

Participants will be screened for contraindications prior to enrollment and monitored throughout the study. Adverse events will be documented and reviewed by the study team. The study has received approval from an Institutional Review Board, and all participants will provide written informed consent prior to participation.
